### **C4. Hotel**

The Hotel Phase portion of this study will take place at a local Charleston hotel. The hotel will be chosen using the following criteria: 1) allows smoking in select hotel rooms that will be used for participants' guest rooms, 2) is in a relatively remote area of Charleston (few businesses within walking distance), 3) has a meeting area that can be utilized by the study for the purposes of data collection and serving meals, 4) in the appropriate price range. Amenities such as a daily free breakfast and hotel gym are preferred but not required. Hotel staff will not be involved in data collection, and will interact with the participants only to the extent necessary (providing with room keys, etc). We have arranged to have this study conducted at the Quality Inn Coliseum in North Charleston. In the event that we need to choose another hotel, we will use the criteria above.

Study staff will search participants' belongings prior to being transported to the hotel, and any non-study tobacco products or alcohol will be confiscated and returned upon completion of that hotel phase. Participants who bring any illegal substances, or weapons to the lab on the day of departure to the hotel will be dismissed from the study. Participants will be transported to and from the hotel by a shuttle service.

Participants will be asked to remain on hotel property and will not be permitted to have any outside visitors. Each participant will receive their own hotel room, unless two participants know each other and request a room together prior to starting the study. Participants will be provided with all meals in the hotel either by the hotel or using an outside catering company. We will provide entertainment (e.g., books, movies, crafts, area to socialize) but participants will be encouraged to bring laptops, cell phones, and other items for down time between study tasks. The hotel is a strength of the proposed protocol because it allows us to investigate the impact of nicotine reduction in a comfortable and social context that mimics the “real world” in which people smoke. Study tasks will take place in a hotel meeting or activity room, or a separate guest room if a hotel meeting room is not available. Two or more staff members will be at the hotel at all times. Participants will be required to remain in their hotel rooms between 9:00PM and 7:00AM unless there is an emergency (e.g., fire). We have successfully utilized these procedures in our previous study to restrict access to non-study tobacco products (1).

### **C5. Instructions**

Participants will be told that while in the hotel, they will be permitted to use research cigarettes provided to them, but that they will not be permitted to use other nicotine or tobacco products. During their screening session, participants will be told that we are investigating a range of nicotine contents and that they will receive cigarettes with different nicotine contents during their two hotel stays. When participants arrive at the hotel, they will be told the condition for that week.

### **C6. Product Distribution**

Participants will have the opportunity to “purchase” Spectrum cigarettes at each “check in” from study staff using a study bank. Each cigarette will cost \$0.30 (close to the national average for cigarettes). Participants will begin the study with \$72.00 (enough for 60 CPD) to spend on cigarettes during the hotel stay, and will be told that any money they choose not to spend on cigarettes will be given to them at the end of the study. Participants do not have to purchase any cigarettes, and if a participant chooses to abstain from smoking while in the hotel, it will not affect their study participation or financial compensation in any way.

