## TRIAL PROTOCOL

**NCT NUMBER:** 03311646

**Document Date:** 7/24/2018

**MUSC IRB Protocol #:** Pro00069959

**Title:** Impact of exclusive use of low nicotine cigarettes on compensatory smoking

**Principal Investigator:** [name]

**NOTE:** Protocol is Version 6 and is the final approved IRB protocol. Two protocol changes are not reflected but were implemented for all study participants: 1) intervention order was fixed for all participants (NNC→VLNC) rather than counterbalanced, and 2) unblinding wording for participants was changed to either “All of the cigarettes provided to you and all other participants during this hotel stay have a normal nicotine content. The nicotine content is about the same as what would be available in a typical cigarette purchased on the market today” (NNC) or “All of the cigarettes provided to you and all other participants during this hotel stay have a very low nicotine content. The nicotine content is about 97% less than what would be available in a typical cigarette purchased on the market today” (VLNC).

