### **C7. Procedures**

Study participation consists of a screening visit and two four-night stays in the hotel.

**C7a. Screening visit.** After obtaining informed consent, screening assessments will be completed (measures described below). At the end of the session, eligible participants will be scheduled for two hotel stays. It will be stressed to participants that it is critical that they attend both hotel stays, and we have provided a completion bonus to maximize the likelihood of study completion. In our prior study (1), 100% of our participants completed the entire hotel protocol. A baseline puff topography assessment will be completed for eligible participants using participants’ usual brand cigarette. Puff topography provides an analysis of smoking behavior including changes in the rate or volume of inhalation which can influence smoke exposure and nicotine delivery of cigarettes.

**C7b. Hotel phase.** Participants will return to the lab on the morning of each hotel stay. Participants will complete a Timeline Follow Back Assessment about their tobacco use over the previous 14 days, and we will collect a first void urine for baseline assessment. We will also obtain an expired carbon monoxide sample.

Participants will arrive at the hotel and have their first opportunity to buy cigarettes at 4PM on Hotel Day 1. While at the hotel, participants will have “check in” times of 8AM, 12PM, 4PM, and 8PM. Check-ins will be used to collect physiological assessments, collect self-report questionnaires, and for participants to purchase more cigarettes if needed. Measures at the hotel are designed to assess the safety of the participants using the study product, the impact of nicotine reduction on physiological and behavioral measures of smoke exposure, and the impact of nicotine reduction on other key measures like withdrawal, craving, and reinforcement value. Participants will return all unused cigarettes and depart the hotel at 12PM on Hotel Day 5. Participants will spend approximately 96 hours (four 24-hr periods) in the hotel. A puff topography assessment will be completed each day by having participants smoke one of the research cigarettes through a device that measures how they smoke cigarettes. Puff topography provides an analysis of smoking behavior including changes in the rate or volume of inhalation which can influence smoke exposure and nicotine delivery of cigarettes.

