17. Wisconsin Inventory of Smoking Dependence Motives (WISDM) Brief V1: A validated measure of nicotine dependence. At baseline, participants complete this questionnaire about their smoking habits.
18. Wisconsin Inventory of Smoking Dependence Motives (WISDM) Brief V2: A validated measure of nicotine dependence. At the end of the hotel week, participants complete this questionnaire but are instructed to only think about their smoking over the last 24 hours.
19. Knowledge and Beliefs about Nicotine: A measure assessing participants knowledge and perceptions of nicotine as an addictive constituent in tobacco and about the health consequences of nicotine
20. Knowledge and Beliefs about Smoking: A measure assessing participants' knowledge and perceptions about the health consequences of smoking
21. Delay Discounting: A validated measure of impulsivity in which participants make hypothetical decisions about whether they would prefer a small amount of money now or a larger amount of money after a variable length of time.
22. End of Hotel Week Assessment After participants have been paid for study participation during each hotel week, they will complete one additional assessment that assessed their use of non-study tobacco products during the hotel week.

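### As written, C6 pays out unspent bank money only at the end of the study, so with a fixed order the saving from not buying is delayed in the NNC stay but not in the VLNC stay; state that the bank is issued and settled per stay

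*Combined protocol and SAP*

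**What the plan says.** C6 (Product Distribution) sets one price, "Each cigarette will cost \$0.30", with no distinction by stay or condition. On the grant it says: "Participants will begin the study with \$72.00 (enough for 60 CPD) to spend on cigarettes during the hotel stay". On the payout, participants "will be told that any money they choose not to spend on cigarettes will be given to them at the end of the study". The grant sentence therefore refers both to the study and to a single hotel stay, and the payout sentence refers to the study.

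C7 (Procedures) says: "Study participation consists of a screening visit and two four-night stays in the hotel". C7b puts each stay at about 96 hours, and C12 divides total hotel cigarettes by 4 to obtain CPD. The note on the title page says that the "intervention order was fixed for all participants (NNC→VLNC) rather than counterbalanced". Item 22 of the measures list (End of Hotel Week Assessment) places that assessment "After participants have been paid for study participation during each hotel week", so some payment is made at each stay. It does not say whether unspent bank money is part of that payment.

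C11a makes cigarettes purchased minus cigarettes returned a primary outcome. A4 and B explain that the bank is there to put a realistic cost on smoking and to avoid a ceiling that could hide compensation.

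**The concern.** The bank discourages buying only because an unspent $0.30 comes back to the participant. When it comes back is part of the incentive. If savings from both stays are paid after stay 2, a cigarette not bought in stay 1 is rewarded after the between-stay gap and the whole of stay 2, whereas one not bought in stay 2 is rewarded within days. Money that arrives later is usually worth less to the person deciding, so the deterrent would be weaker in stay 1.

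Under counterbalancing, this would fall on both conditions. With the order fixed, stay 1 is always NNC and stay 2 always VLNC. The expected effect is more NNC buying relative to VLNC. That works against the main hypothesis and towards the stated alternative, on a purchase-based primary outcome, and expired CO depends on the amount smoked. C13 says that only nicotine content and the information about it differ between conditions; a difference in payment timing would be a third thing that differs. What participants are told matters here as much as what staff intend, because purchases respond to the rule as participants understand it.

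**Working it through.** **1. Reproduce the plan's figure.** Inputs from C6: bank $72.00, price $0.30. Cigarettes affordable = 72.00/0.30 = 240.

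| Days covered | CPD = 240/days | Matches the stated 60? |
|---|---|---|
| 4 (one stay, C7b and C12) | 60 | yes |
| 5 (calendar days of one stay) | 48 | no |
| 8 (both stays) | 30 | no |

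The 60 CPD figure holds only for one bank per four-day stay. Covering 60 CPD in both stays would take 60 × 8 × 0.30 = $144.00. C6's own arithmetic thus points to a $72.00 bank per stay, and only the phrase about beginning the study points the other way.

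**2. Timing under each reading of the payout rule, with a bank per stay.**

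| Rule | Stay 1 savings (all NNC) | Stay 2 savings (all VLNC) |
|---|---|---|
| As written: paid at the end of the study | wait for the gap and stay 2 | paid at about the end of stay 2 |
| Paid with each week's payment | paid at the end of stay 1 | paid at the end of stay 2 |

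Up to $72.00 per person is affected in stay 1. Only the first rule creates a difference between stays.

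**3. Can the model remove it?** C12 and section 3c of the Data Safety Monitoring Plan specify fixed effects for nicotine content, period and order. With NNC always first, period takes the same values as nicotine content and order is constant, so neither term separates payment timing from nicotine. The baseline measures that C12 allows as covariates describe smoking before the stay, not the payout rule.

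**4. Size.** The documents give neither the gap between stays nor a discount rate, so the following is an illustration on assumed values only. With hyperbolic discounting, the present-value price in stay 1 is 0.30/(1 + kD), where k is the daily discount rate and D the extra delay in days.

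| Assumed k | Assumed D | 0.30/(1 + kD) | Change |
|---|---|---|---|
| 0.001 | 7 | $0.298 | −0.7% |
| 0.01 | 14 | $0.263 | −12.3% |
| 0.05 | 30 | $0.120 | −60.0% |

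The range runs from negligible to large. Turning it into cigarettes would also need a price response, which the documents do not give.

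**The case against.** The strongest reply is that this is loose wording, not a demonstrated bias.

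- **The price is the same.** It is $0.30 in both stays. A reader might infer that cigarettes actually carried different effective prices. The documents do not establish that: it requires both that stay 1 money was held until after stay 2 and that participants discounted the delay. This stands.
- **A shared bank is contradicted.** A reader might also infer that one $72.00 bank covered both stays, giving an average ceiling of 30 CPD, below the 30.9 CPD seen on VLNC in the prior hotel study. The 60 CPD figure and the singular reference to the hotel stay contradict this, and it would defeat the bank's stated purpose. The comparison is also weak: 30.9 CPD came from a study with free cigarettes, and it sets a VLNC mean against an average over both conditions. At that study's baseline of 20.1 CPD, stay 1 would cost 20.1 × 4 × 0.30 = $24.12, leaving $47.88, or about 39.9 CPD for stay 2. This stands, and the ceiling is not part of the point.
- **Payment is made each week.** Item 22 is compatible with weekly settlement of the bank, and parts of the protocol between C7c and the measures list are not visible. This stands as a limit on certainty: the missing text cannot be counted as a gap. C6 nevertheless states a payout rule that participants are to be told, and that rule differs from weekly settlement.
- **Fixed order is the root cause.** True: it confounds every difference between stays with condition. This one, however, can be removed by wording alone.

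**Conclusion.** The point holds as a design weakness in a stated rule, not as a proven bias. If the C6 payout rule was followed as written, the reward for not buying was delayed in the all-NNC stay and nearly immediate in the all-VLNC stay, and the planned analysis cannot separate that from nicotine content. The direction, towards relatively more NNC purchasing, rests on the ordinary assumption that people value delayed money less. The size is undetermined, and the 0.7% to 60.0% range reflects assumed inputs.

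A reader might go further and attribute a finding of no compensation to the payment timing. The documents do not support that, since they show neither how the bank was settled nor how strongly participants responded to it. Independently of timing, C6 should be reconciled with itself: granting the bank at the start of the study does not fit 60 CPD across two stays.

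**What to change.** In C6, and in the script read to participants at both stays, state that $72.00 is credited at the start of each hotel stay (240 cigarettes, 60 CPD over four days), that the unspent balance for that stay is paid at its end together with that week's payment, and that nothing carries over.

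The cost is one sentence in C6 and one line in the script. If the bank was always meant to be per stay, the total paid does not change. The drawback is that some money is paid earlier, which slightly weakens the incentive to return for stay 2; the completion bonus in C7a offsets this.

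The title-page note describes the fixed order as already implemented for all participants, so the wording change may come too late. In that case, report how the bank was issued and settled and what participants were told. If settlement came only after stay 2, list it as a period difference confounded with condition when interpreting the cigarette count and CO. If other protocol text already provides for settlement at each stay, aligning C6 with it is enough.

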### **C7. Procedures**

Study participation consists of a screening visit and two four-night stays in the hotel.

**C7a. Screening visit.** After obtaining informed consent, screening assessments will be completed (measures described below). At the end of the session, eligible participants will be scheduled for two hotel stays. It will be stressed to participants that it is critical that they attend both hotel stays, and we have provided a completion bonus to maximize the likelihood of study completion. In our prior study (1), 100% of our participants completed the entire hotel protocol. A baseline puff topography assessment will be completed for eligible participants using participants’ usual brand cigarette. Puff topography provides an analysis of smoking behavior including changes in the rate or volume of inhalation which can influence smoke exposure and nicotine delivery of cigarettes.

**C7b. Hotel phase.** Participants will return to the lab on the morning of each hotel stay. Participants will complete a Timeline Follow Back Assessment about their tobacco use over the previous 14 days, and we will collect a first void urine for baseline assessment. We will also obtain an expired carbon monoxide sample.

Participants will arrive at the hotel and have their first opportunity to buy cigarettes at 4PM on Hotel Day 1. While at the hotel, participants will have “check in” times of 8AM, 12PM, 4PM, and 8PM. Check-ins will be used to collect physiological assessments, collect self-report questionnaires, and for participants to purchase more cigarettes if needed. Measures at the hotel are designed to assess the safety of the participants using the study product, the impact of nicotine reduction on physiological and behavioral measures of smoke exposure, and the impact of nicotine reduction on other key measures like withdrawal, craving, and reinforcement value. Participants will return all unused cigarettes and depart the hotel at 12PM on Hotel Day 5. Participants will spend approximately 96 hours (four 24-hr periods) in the hotel. A puff topography assessment will be completed each day by having participants smoke one of the research cigarettes through a device that measures how they smoke cigarettes. Puff topography provides an analysis of smoking behavior including changes in the rate or volume of inhalation which can influence smoke exposure and nicotine delivery of cigarettes.

**C7c. End of Study Procedures:** After a participant has completed all study procedures during the second hotel week and has been paid for participation, a research assistant should read the following script:

6. Questionnaire of Smoking Urges—Study Cigarette: which measures the urge to smoke participants' assigned study cigarette.
7. Cigarette Evaluation Scale—Usual Brand: which measures responses to participants' usual brand cigarettes (e.g., reward satisfaction)
8. Cigarette Evaluation Scale—Study Cigarette: which measures responses to participants' assigned study cigarettes (e.g., reward satisfaction)
9. Cigarette Purchase Task—Usual Brand: will be used to generate demand curves. The Cigarette Purchase Task is considered to be a measure of reinforcement value. Participants report the number of usual brand cigarettes that they would consume in a day if cigarettes were a variety of prices.
10. Cigarette Purchase Task—Study Cigarette will be used to generate demand curves. The Cigarette Purchase Task is considered to be a measure of reinforcement value. Participants report the number of assigned study cigarettes that they would consume in a day if cigarettes were a variety of prices.
11. Perceived Health Risks—Usual Brand: a measure of the perceived health risks of participants' usual brand cigarette
12. Perceived Health Risks—Study Cigarette: a measure of the perceived health risks of participants' assigned study cigarette
13. Predicted Behavior Questionnaire: a questionnaire designed to assess participants predictions about their tobacco use if the research cigarettes were the only cigarettes available for purchase (a potential policy scenario).
14. Smoking Consequences Questionnaire-Adult is a validated measure of smoking expectancies and will be used to assess participants expectancies for very low nicotine content and normal nicotine content research cigarettes.
15. Fagerstrom Test for Nicotine Dependence (FTND) V1: A validated measure of nicotine dependence. At baseline, participants complete this questionnaire about their smoking habits.
16. Fagerstrom Test for Nicotine Dependence (FTND) V2: A validated measure of nicotine dependence. At the end of the hotel week, participants complete this questionnaire but are instructed to only think about their smoking over the last 24 hours.
17. Wisconsin Inventory of Smoking Dependence Motives (WISDM) Brief V1: A validated measure of nicotine dependence. At baseline, participants complete this questionnaire about their smoking habits.
18. Wisconsin Inventory of Smoking Dependence Motives (WISDM) Brief V2: A validated measure of nicotine dependence. At the end of the hotel week, participants complete this questionnaire but are instructed to only think about their smoking over the last 24 hours.
19. Knowledge and Beliefs about Nicotine: A measure assessing participants knowledge and perceptions of nicotine as an addictive constituent in tobacco and about the health consequences of nicotine
20. Knowledge and Beliefs about Smoking: A measure assessing participants' knowledge and perceptions about the health consequences of smoking
21. Delay Discounting: A validated measure of impulsivity in which participants make hypothetical decisions about whether they would prefer a small amount of money now or a larger amount of money after a variable length of time.
22. End of Hotel Week Assessment After participants have been paid for study participation during each hotel week, they will complete one additional assessment that assessed their use of non-study tobacco products during the hotel week.

**The following questionnaires will be completed as an interview and entered into Redcap by study staff:**

1. Tobacco Use History Questionnaire: which measures variables such as smoking amount, cigarette brand, age of initiation, number of quit attempts, duration of quit attempts, and duration of smoking
2. Smoking Cessation Questionnaire to assess use of nicotine replacement therapy or smoking cessation medications to help participants quit smoking
3. Drug Use Questionnaire 12 + 1 month: measures drug use over the last 12 months and 1 month
4. Health Changes Questionnaire V1: assesses health changes since participant's last visit
5. Health Changes Questionnaire V2: assesses health changes since entering the hotel.
6. Timeline Followback: assesses tobacco use in the last two weeks.
7. Mini International Neuropsychiatric Interview (MINI) suicide subscale: to evaluate suicide risk
8. Brief Medical History: to assess current diagnoses, symptoms, and past health problems

9. Follow-up Call: Approximately 30 days after the end of the second hotel week, study staff will call each participant and complete a short follow-up call. During this call, we will assess current tobacco use and any quit attempts since the study ended. We will also ask participants whether they used any non-study tobacco products during their hotel stays. If participants self-report non-study tobacco use while at the hotel, we will ask about the frequency and rate of use, which products were used, and how participants obtained those products. Participants will be paid for the call regardless of whether they self-report non-study tobacco product use.

**The following questionnaires will be completed as an interview, tape recorded with the permission of the participants, and transcribed later:**

1. Qualitative Interview: In order to better understand participants' subjective experiences in the hotel and their opinions and reactions to a potential regulatory nicotine reduction policy, a 15-20 minute qualitative interview will be completed.

